## **4 SELECTION AND ENROLLMENT OF PARTICIPANTS**

### **4.1 Study Enrollment Procedures**

#### **4.1.1 Screening**

Patients will be identified for screening via diagnosis codes for AF on chart review. This can be easily identified by querying current electronic medical record systems. If needed, patients with ICMs can be identified by lists maintained at each study center of those who undergo ICM insertion.

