## **3 STUDY DESIGN**

We propose a multi-center, retrospective study to evaluate the use of ICM versus traditional, non-ICM methods such as ECGs, Holter, and mobile cardiac outpatient telemetry (MCOT) units, referred to as non-ICM from here on out, from 2018 to 2021. The primary outcome will be the evaluation of AF freedom at 12 months with continued AAD and OAC use. Secondary outcomes are described above. This study will be approved by the Institutional Review Board (IRB), and patient consent will not be required due to the nature of the study.

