#### **4.1.2 Consent and Enrollment**

Patients who meet inclusion and exclusion criteria after screening will be directly enrolled in the study. No randomization will occur, but patients will be separated into an ICM and non-ICM arm. We will enroll approximately 2500 patients [n=1250 (ICM) and n=1250 (non-ICM)] from 2018-2021. No consent will be required due to the nature of the study.

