### **4.2 Inclusion Criteria**

- Patients > 18 years of age
- Present for management of AF
- ICM is inserted at the discretion of the treating physician

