### **4.3 Exclusion Criteria**

- Patients < 18 years of age
- Presence of a permanent pacemaker, implantable cardiac defibrillator, or cardiac resynchronization therapy
- Unable to tolerate ICM or traditional monitoring with ECG, Holter, or MCOT monitoring
- Unable to tolerate AAD, OAC, and CA as part of AF standard of care
- ICM inserted for cryptogenic stroke or syncope
- Was not followed > 12 months
- CA performed for AF before ICM implant

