## 6 STUDY PROCEDURES

### 6.1 Description of Evaluation

*Table 1. Variables for data collection will include but are not limited to the following.*

Variables	Description and Definition
Age	## Years
Gender	0 = Male, 1 = Female
BMI	## kg/m2
Race	0 = Caucasian, 1 = African American, 2 = Hispanic, 3 = Asian, 4 = Other
Hypertension	0 = No, 1 = Yes
Hyperlipidemia	0 = No, 1 = Yes
Diabetes Mellitus	0 = No, 1 = Yes
Coronary Artery Disease	0 = No, 1 = Yes
CVA/TIA	0 = No, 1 = Yes
Peripheral Artery Disease	0 = No, 1 = Yes
Obstructive Sleep Apnea	0 = No, 1 = Yes
Compensated HF (EF > 35%)	0 = No, 1 = Yes
History of Smoking	0 = No, 1 = Yes
Thyroid Dysfunction	0 = None, 1 = Hypothyroidism, 2 = Hyperthyroidism
Chronic Obstructive Pulmonary Disease	0 = No, 1 = Yes
Gastrointestinal Disorders	0 = No, 1 = Yes
CHADS 2 /VASC 2 Score	##
Antiarrhythmic Drug	
History of Cardioversion	0 = No, 1 = Yes
Baseline AAD Use	0 = No, 1 = Yes
Duration of Arrhythmia	## Mos.
Left Atrial Size	## cm.
Left Ventricular Ejection Fraction	## %
Access to EP	0 = No, 1 = Yes
Compliance to OAC	0 = No, 1 = Yes
Attempted AAD	0 = No, 1 = Yes
Need for Catheter Ablation	0 = No, 1 = Yes
Time to Catheter Ablation	## Days
Number of Monitors used Post-CA	##

Type of Monitors Used	0 = MCOT, 1 = 48-Hr Holter
Need for Redo Ablation	0 = No, 1 = Yes
Time to Redo Ablation	## Days
CV-Related Hospital Duration	## Days
Length of Stay	## Days
AF-Related Hospitalization	0 = No, 1 = Yes
HF-Related Hospitalization	0 = No, 1 = Yes
Bleeding Complication	0 = No, 1 = Yes
Stroke and TIA	0 = No, 1 = Yes
Freedom of AF at 12 Mos.	0 = No, 1 = Yes
Continued OAC Use	0 = No, 1 = Yes
Continued AAD Use	0 = No, 1 = Yes

Abbreviations: BMI – body mass index, CVA = cerebrovascular accident, TIA – transient ischemic attack, AAD = antiarrhythmic drug, CV – cardiovascular, CA = catheter ablation, AF – atrial fibrillation, HF – heart failure, OAC – oral anticoagulation, MCOT – mobile cardiac outpatient telemetry

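### AF status at entry is neither required nor among the listed variables, so a difference between the arms in patients already free of AF at entry could pass unadjusted into AF freedom at 12 months

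*Combined protocol and SAP*

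**What the plan says.** **Entry.** Section 4.1.1 states: "Patients will be identified for screening via diagnosis codes for AF on chart review". It gives no date window and asks for no confirming tracing. The one inclusion criterion in section 4.2 that concerns AF itself is "Present for management of AF". Under section 4.1.2, "Patients who meet inclusion and exclusion criteria after screening will be directly enrolled in the study". The section 4.3 exclusions cover age, implanted devices, tolerance of monitoring and treatment, ICM for cryptogenic stroke or syncope, follow-up ("Was not followed > 12 months") and prior ablation ("CA performed for AF before ICM implant"). None of them requires recent AF.

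**Data.** The Table 1 baseline fields closest to rhythm are "Duration of Arrhythmia", history of cardioversion and baseline AAD use. AF type, rhythm at entry, AF burden and date of last documented AF are not listed. The table caption says the list is not exhaustive.

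**Outcome.** Section 3 states: "The primary outcome will be the evaluation of AF freedom at 12 months with continued AAD and OAC use". Table 1 holds it as one yes/no field, "Freedom of AF at 12 Mos", with no definition. Section 5.1 also reviews charts for arrhythmia recurrence over 12 months, and section 9.3 lists recurrence, not AF freedom, among the primary outcomes.

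**Comparison.** There is no randomization (section 6.2). ICM insertion is at the treating physician's discretion (section 4.2) and depends on physician preference (section 2.2). Section 9.4 plans t-tests, Mann-Whitney tests, chi-square tests and Cox models, and names no covariates.

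**The concern.** Freedom from AF at 12 months depends strongly on whether the patient had active AF at the start. A patient with an old code who presents for AF management in stable sinus rhythm is eligible. If that patient stays in sinus rhythm, the chart is scored as AF-free whichever monitor was used.

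If such patients were equally common in both arms, they would only dilute a true effect. Here nothing makes them equally common. The physician decides who receives an ICM, and active AF is a plausible reason to implant one, although the documents do not say so. The exclusion of ablation before ICM implant, read literally, removes previously ablated patients from the ICM arm and leaves them eligible in the other.

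The result could be a significant difference in AF freedom that reflects who was chosen for an ICM. A confounder that is not collected cannot be adjusted for in the analysis.

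**Working it through.** **1. The plan's own figure.** Section 9.2 states 99% power with 2500 patients, 1250 per arm, and assumes no difference in AAD, OAC or CA use. It gives no AF-freedom rate and no effect size, so the 99% cannot be reproduced. Under a true zero difference, a two-sided test at 0.05 rejects 5% of the time. Solving backwards, 99% would fit, for example, 50% v 58.5%. That pair is not in the plan. It shows only that at 1250 per arm a difference of a few points has a fair chance of reaching p < 0.05, whether or not monitoring caused it.

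**2. Inputs for the bias check.** From the plan: n = 1250 per arm (section 9.2) and significance at p < 0.05 (section 9.4), taken as two-sided. The rest are assumptions, because the documents give no figures:

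- q, share AF-free at entry: 10% in the ICM arm, and 20% or 30% in the non-ICM arm.
- s, share of these still scored AF-free at 12 months: 80% or 90%, the same in both arms.
- p, success in all other patients: 50%, the same in both arms, so monitoring has no effect.

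**3. Formulas.** AF freedom in an arm = q × s + (1 − q) × p. The false difference is therefore (q_non-ICM − q_ICM) × (s − p). The chance of a significant result is about Φ(d/SE − 1.96), with SE = √[(a(1 − a) + b(1 − b))/1250], where a and b are the two arms' rates and d = b − a.

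**4. Numbers.** ICM arm, q = 10%: 0.10 × 0.80 + 0.90 × 0.50 = 53% with s = 80%, and 0.09 + 0.45 = 54% with s = 90%.

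| Non-ICM q | s | ICM | Non-ICM | False difference | SE | d/SE − 1.96 | P(p < 0.05) |
|---|---|---|---|---|---|---|---|
| 20% | 80% | 53% | 0.16 + 0.40 = 56% | 3 points | 1.99 points | −0.45 | about 33% |
| 20% | 90% | 54% | 0.18 + 0.40 = 58% | 4 points | 1.98 points | 0.06 | about 52% |
| 30% | 80% | 53% | 0.24 + 0.35 = 59% | 6 points | 1.98 points | 1.07 | about 86% |
| 30% | 90% | 54% | 0.27 + 0.35 = 62% | 8 points | 1.97 points | 2.11 | about 98% |

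A valid test of no monitoring effect would reject 5% of the time in every row.

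**5. Equal shares, for contrast.** If the same share f were AF-free at entry in both arms and all stayed free, a true difference would shrink by the factor (1 − f). Starting from 50% v 58.5%, f = 10% leaves 7.7 points (power about 97%) and f = 30% leaves 6.0 points (about 89%). This is dilution only. The bias in step 4 arises from imbalance between arms.

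**The case against.** Much of the opposing case is sound and limits the point.

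- **Scoring is not automatic.** A reader might infer that every patient AF-free at entry counts as a success. The documents do not support that. AF freedom is undefined, sections 5.1 and 9.3 track recurrence, and a relapse could make such a patient a failure. The calculation lets 10-20% of them fail.
- **Sinus rhythm is a normal start for time to recurrence.** This is true of the Cox and Kaplan-Meier analyses in section 9.4. It does not remove confounding, because patients with and without active AF at entry can be expected to recur at different rates.
- **The list in Table 1 is open.** A site could collect entry rhythm, and the listed fields are weak proxies. But an open list commits no center to collecting it.
- **Paroxysmal AF missed by short recordings.** One might add that a single ECG or a 48-hour recording often misses intermittent AF. That is an ascertainment question. No entry rule changes it, and it is not counted here.
- **ICMs detect more AF.** Section 2.1 says so for the settings it cites, so the monitoring method can change how the same patient is classified. This is a separate problem, which could add to this one.
- **This is one confounder among several.** That is fair. It is singled out because it is so close to the outcome and has no listed field.
- **A mandatory look-back has costs.** It would drop controlled patients who matter for continued AAD and OAC use, and documented AF depends on how closely the patient was monitored before entry. This objection stands, and the fix follows it.

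**Conclusion.** The concern holds as a risk of confounding by AF status at entry. No criterion requires recent AF, no listed variable identifies patients already AF-free, and no adjustment is specified in a comparison where physicians choose the monitor. The wording of the prior-ablation exclusion is the one place where the text itself treats the two arms' entry status differently. That this raises the AF-free share in the non-ICM arm is plausible but not shown.

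The size is unknown. The 3-4 points (significant 33-52% of the time) and 6-8 points (86-98%) rest wholly on the assumed shares and success rates, and the larger pair needs a 20-point imbalance for which the documents give no evidence. A reader might infer that the trial's result will be false, or that AF-free entrants inflate both arms by a known amount. Neither follows from the documents. The study should correct this, since the omission is cheap to repair in a chart review.

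**What to change.** 1. **Table 1:** for both arms, add AF type, rhythm at entry and date of last documented AF before entry. State the date that counts as entry in each arm.
2. **Section 9.4:** adjust the AF-freedom and recurrence comparisons for baseline AF status, and report them separately for patients AF-free and not AF-free at entry.
3. **Sections 3 and 9.3:** define AF freedom over a stated interval ending at month 12, and use the same definition in both places.
4. **Section 4.3:** reconcile the prior-ablation exclusion across the two arms, or explain why it applies to one.
5. **Sensitivity analysis:** repeat the comparison in patients with AF documented within a stated look-back window. Do not make this an entry rule.

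The cost is a few extra chart fields per patient and some missing values. One weakness remains: baseline AF status depends on how intensively each patient was monitored before entry, so adjustment will reduce the confounding but may not remove it.

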#### **4.1.2 Consent and Enrollment**

Patients who meet inclusion and exclusion criteria after screening will be directly enrolled in the study. No randomization will occur, but patients will be separated into an ICM and non-ICM arm. We will enroll approximately 2500 patients [n=1250 (ICM) and n=1250 (non-ICM)] from 2018-2021. No consent will be required due to the nature of the study.

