## **2 BACKGROUND AND RATIONALE**

### **2.1 Background on Condition, Disease, or Other Primary Study Focus**

AF is the most frequent cardiac arrhythmia, with a global prevalence that is only expected to increase. A significant number of patients – up to 38% – may be asymptomatic, making management more difficult. [1] Regardless of symptoms, AF is associated with significant morbidities, including but not limited to heart failure, stroke, dementia, and death.

The management of AF is complex, with clinical decisions related to rate and rhythm control strategies with AADs and CA and stroke prevention. Like other chronic diseases, frequent routine assessments help select, assess, and change management strategies. Implantable cardiac monitors (ICMs) are another option that store electrocardiogram (ECG) tracings for years at a time, enabling continuous monitoring, assessment of AF burden, and therapy efficacy. Previous studies have demonstrated a threefold increase in AF detection, including asymptomatic AF in cryptogenic stroke, syncope, and after CA. using ICMs.[2-4] Their use in AF management has gained popularity for this reason.

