### **2.2 Study Rationale**

Even with its increasing popularity and use, the impact of ICMs on AF management is still being determined and can even be conflicting. Furthermore, the use of ICM is dependent on physician preference. We hypothesize that dynamic monitoring with ICMs is superior to conventional methods and should be used for all patients with AF. Thus, we aim to measure the outcomes of using ICM versus more traditional approaches in patients with AF.

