## 9.2 Sample Size and Randomization

We will aim for 2500 enrolled participants to result in a 99% power for statistical significance, assuming no difference in AAD, OAC, or CA use rates between those with ICM and non-ICM monitoring methods. We cannot control the exact number of subjects but will attempt a 1:1 allocation into the ICM and non-ICM arms to result in 1250 patients each.

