## 9.4 Data Analyses

Statistical analysis will be performed on both continuous and categorical variables. As appropriate, continuous variables will be reported as mean  $\pm$  standard deviation and compared with two-tailed T-tests and Mann-Whitney testing. Categorical variables will be reported as frequency and percentages and compared with Chi-square testing as appropriate. Cox proportional regression models will be used for hazard ratios and confidence intervals. A p-value  $< 0.05$  will be used to determine statistical significance. Kaplan-Meier graphs will be calculated when appropriate. We will use SPSS [IBM, Armonk, New York] for all statistical analysis.

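### Calendar year is a plausible uncontrolled confounder: ICM use is said to be rising, 2018-2021 is pooled, and neither chart selection nor the analysis takes account of index year

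*Combined protocol and SAP*

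**What the plan says.** All references are to the combined protocol and SAP.

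- **Window and quotas.** Section 4.1.2: "We will enroll approximately 2500 patients [n=1250 (ICM) and n=1250 (non-ICM)] from 2018-2021". Section 9.2 treats the ratio as a target for the study as a whole: "We cannot control the exact number of subjects but will attempt a 1:1 allocation into the ICM and non-ICM arms". Nothing is said about balance within a year.
- **Trend in ICM use.** Section 2.1: "Their use in AF management has gained popularity for this reason". Section 2.2: "Even with its increasing popularity and use, the impact of ICMs on AF management is still being determined and can even be conflicting". No figures by year or by site are given.
- **Arm assignment.** There is no randomization. Section 4.2: "ICM is inserted at the discretion of the treating physician".
- **Data.** Table 1 in section 6.1 lists durations, such as days to ablation, but no index, enrolment or implant date or year. The list is open-ended: "Variables for data collection will include but are not limited to the following".
- **Analysis.** Section 9.4 names t-tests, Mann-Whitney tests, Cox models and Kaplan-Meier curves, and for categorical data: "Categorical variables will be reported as frequency and percentages and compared with Chi-square testing as appropriate". It names no covariate, stratum, matching or calendar term.

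**The concern.** Calendar time can confound this comparison through two links. One runs from year to arm: if ICM use was growing at the study centres, the ICM arm may have a later year mix than the non-ICM arm. The other runs from year to outcome. Most primary outcomes in section 9.3 are practice decisions (AAD and OAC initiation, time to ablation, drug changes after ablation, redo ablation), and section 6.3 leaves management to the treating physician. Such outcomes can move over four years whatever monitor is used.

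If both links are present, the pooled contrast mixes the effect of the monitor with the effect of the year. A large sample does not help, because it shrinks the standard error and not the bias. Adjusting for every variable listed in Table 1 would not remove the problem either, since year is not among them. As listed, the dataset could not even show a reader whether the two arms are contemporaneous.

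**Working it through.** **The plan's own figure.** The only design figure is the 99% power in section 9.2. It cannot be reproduced, because no effect size or outcome rate is given; under the stated assumption of no difference, a 5% test rejects 5% of the time. The point here does not depend on that figure.

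**Inputs from the documents.** 1250 per arm (4.1.2, 9.2); four entry years pooled; significance at 0.05 (9.4), taken as two-sided throughout, although 9.4 says so only for the t-test.

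**Assumptions, not in the documents.** Equal total entry per year; an outcome rate of about 30%; no true ICM effect; linear drift of 2 or 5 percentage points per year; an ICM share of entrants that rises linearly over 2018-2021 and averages 50%.

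**Formulae.**
- Gap = mean index year in the ICM arm minus mean index year in the non-ICM arm.
- Spurious difference = gap × yearly drift.
- SE = √(2 × 0.3 × 0.7 / 1250) = √0.000336 = 1.83 points.
- False-positive rate = P(Z > 1.96 − d/SE) + P(Z < −1.96 − d/SE), where d is the spurious difference.

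**Gap for an ICM share of 35, 45, 55, 65%.** With years coded 0 to 3, the ICM arm is spread 17.5, 22.5, 27.5, 32.5% and the non-ICM arm is the reverse. The means are 0.225 + 0.550 + 0.975 = 1.75 and 0.275 + 0.450 + 0.525 = 1.25, so the gap is 0.50 year. In the last two years fall 60% of ICM and 40% of non-ICM patients. For d = 1.0 point, d/SE = 0.55 and the rate is 8.5%. For d = 2.5 points, d/SE = 1.36 and the rate is 27.6%.

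**Gap for an ICM share rising from 45 to 55%.** The gap is 1.583 − 1.417 = 0.167 year. Then d = 0.33 or 0.83 points, and the rates are 5.4% and 7.4%.

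| Scenario | Gap (years) | Drift (points/year) | Spurious difference (points) | False-positive rate |
|---|---|---|---|---|
| Same year mix in both arms | 0 | any | 0 | 5.0% |
| No drift | any | 0 | 0 | 5.0% |
| ICM share 45 to 55% | 0.17 | 2 to 5 | 0.3 to 0.8 | 5.4 to 7.4% |
| ICM share 35 to 65% | 0.50 | 1 | 0.5 | 5.9% |
| ICM share 35 to 65% | 0.50 | 2 to 5 | 1.0 to 2.5 | 8.5 to 28% |

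**Other assumptions.** With a 60% starting rate, a gap of 0.34 year (ICM arm 20, 23, 27, 30% by year, non-ICM arm the reverse) and a drift of 1 to 5 points per year, the spurious difference is 0.3 to 1.7 points and the false-positive rate 5.4 to 14.8%. The pattern does not hinge on the 30% rate.

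**The case against.** A reader might infer that ICM patients do come from later years and that changes in AF care will be read as ICM effects. The documents do not support this. Sections 2.1 and 2.2 speak of popularity in general terms. No section gives a year distribution by arm, and none says that AF care changed over 2018-2021. Bias needs both.

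The sampling step also matters. The arms are quotas, not a census. Section 4.1.1 finds patients by diagnosis code and, if needed, ICM patients from centre lists. The year mix of the non-ICM arm therefore depends on which charts are pulled to fill its quota, and no rule for that is given. Rising use makes a later ICM mix plausible but does not settle the size or even the direction of a gap. This objection stands; what remains is that balance by year is not assured.

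A reader might also infer from Table 1 that the year will be unavailable. It is not limited to the listed items, and days to ablation and the follow-up exclusion in section 4.3 already require start dates from the chart. The gap is that year is not prespecified for collection or analysis, not that it cannot be had.

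Steeper assumptions produce alarming figures. An ICM share rising from 20 to 80% gives a one-year gap, 2 to 5 points of bias and a false-positive rate of 19 to 78%. Nothing in the documents supports so steep a rise, and the conclusion does not rest on it.

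Last, section 9.4 plans no covariate adjustment at all, so year is one of several unadjusted confounders and is not shown to be a leading one. That is true. Year still needs separate mention, because the obvious general remedy, adjusting for the baseline variables in Table 1, would miss it.

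**Conclusion.** The point holds as a conditional one. The protocol itself describes a rising exposure, assigns it by physician discretion, pools four years, and has no step in selection, data collection or analysis that protects against calendar-time confounding. Whether there is any bias is unknown, because neither the year mix nor the drift is given. On the assumptions above, the result runs from nothing (5% false positives if either gap or drift is absent) to 1.0-2.5 points (8.5-28%) for a half-year gap with 2-5 points of drift per year. The change should be made because it is cheap and because the charts to be pulled determine the year mix; it is not a demonstration that the planned comparison is biased.

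**What to change.** 1. **Define an index date on the same basis in both arms.** One candidate is the AF-management visit in the window at which the initial monitoring method was chosen. An implant date will not serve, since non-ICM patients have none and section 9.1 lets them cross into the ICM group at any time; the handling of those who cross has to be stated alongside.
2. **Add the index date to Table 1** and report the year mix by arm.
3. **Select non-ICM charts 1:1 within index year** where numbers allow, and fix this rule before the charts are pulled. Identical year mixes make the calendar bias zero whatever the drift.
4. **In section 9.4,** stratify the Cox models by index year, replace the pooled Chi-square with a year-stratified Cochran-Mantel-Haenszel test, and use year-adjusted or year-stratified versions of the t-test and Mann-Whitney comparisons.

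The cost is agreement on an index-date definition, one date per chart, a selection rule and a few sentences in section 9.4. The downsides are that exact 1:1 may not be reached in years with few eligible patients in one arm, and that year adjustment does nothing for the other unadjusted confounders.
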